6.5.3 Deaths and Serious Adverse events

Serious adverse events (SAE) will be classified using Version 5 of the National Cancer Institute (NCI) Common Terminology Criteria Adverse Event (CTCAE) grading system, and MedDRA terminology.

- Overview over treatment-emergent SAEs
- Treatment-emergent SAEs by worst CTCAE grade
- Treatment-emergent SAEs leading to study drug withdrawal
- Treatment-emergent SAEs leading to study termination
- Treatment-emergent SAEs leading to regorafenib dose reduction
- Treatment-emergent SAEs leading to drug interruption
- Treatment-emergent SAEs leading to dose reduction and/or drug interruption
- Overview over treatment-emergent drug-related SAEs
- Treatment-emergent drug-related SAEs by worst CTCAE grade
- Listing of treatment-emergent SAEs
- Listing of non-treatment-emergent SAEs

The incidence of deaths in the study and especially deaths up to within 30 and 100 days of last dose of Regorafenib and Nivolumab respectively will be summarized by cause of death. All deaths up to within 30 (100) days of last dose of study drug will be listed by patient with start and stop date of study medication, date of death, and cause of death. All deaths beyond 30 (100) days after last dose of study drug will be displayed in a separate listing.

6.5.4 Pregnancies

All pregnancies reported during the study will be listed.

6.5.5 Clinical laboratory data

Descriptive statistics (number of observations, mean, standard deviation, minimum, median and maximum values) will be presented for clinical laboratory tests (hematology, clinical biochemistry and urinalysis), their changes from baseline (including baseline value), and their percent changes from baseline at applicable visits.

Severity of hematological and biochemical laboratory values will be assessed based on NCI CTCAE Version 5.0. CTCAE severity grading for laboratory abnormalities are based on applicable laboratory threshold values outlined in NCI CTCAE. It should be noted that in the present analysis of those laboratory parameters for which additional clinical information potentially can also influence the toxicity grade, this clinical information is in general not available and only the laboratory measurements are used for severity assessment.

Any additional specific handling of the NCI CTCAE toxicity grading assignments will be noted in the footnotes of the corresponding tables as applicable per the data collection in the study.

- In the event of overlapping CTCAE criteria ranges for specific lab tests, the algorithm assigns the worst grade
- If calcium type is not recorded (i.e. only “calcium” is recorded), then grading is done as if the calcium is total calcium. “Calcium corrected” is computed from total calcium and serum albumin (if ≤ 4.0 g/dl) from the same time point based on CTCAE v5.0 guidance. If serum albumin (if ≤ 4.0 g/dl) from the same time point is not available or if “calcium, unspecified” was collected then grading is done as if the calcium is “corrected calcium.”
- Results with special characters (such as “>” and “<”) are not graded.

The frequency of treatment emergent laboratory abnormalities regarding hematology, coagulation panel, clinical chemistry, and urinalysis will be tabulated. Worst grades for hematological and biochemical toxicities will be calculated according to CTCAE based on laboratory measurements, and will be summarized by NCI CTCAE category and worst grade.

Clinical laboratory toxicities during treatment including a period of 30 days after last dose of treatment will be considered as “treatment-emergent” for Regorafenib. The duration for Nivolumab will be 100 days.

The last non-missing value before or on the first day of study drug will be retained as “baseline” data. If several assessments are performed on the same day (without timing information) the average of the values will be considered.

Incidence tables (frequency and percentage of patients) as well as tables with change in NCI CTCAE worst grade from baseline will be presented as following:

- Hematological and biochemical toxicity during screening (the last evaluation available before assignment to treatment is taken into account).
- Treatment-emergent hematological and biochemical toxicity.
- Treatment-emergent hematological and biochemical toxicities with incidence rate above 5% in any treatment arm.
- Change in worst grade for hematological and biochemical toxicity from baseline.

The laboratory values will be also categorized into low, normal and high according to their reference ranges.

Descriptive statistics will be calculated by time interval.

Unscheduled laboratory data will be listed (Section 16 of the CSR) only.

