1.2 Schema

This study is composed of the following periods: Screening, treatment, active follow-up (FU), and long-term follow up. Participants will be considered “on study” during screening, treatment, active FU periods, and long-term FU periods. An overview of the study schema is presented in [Figure 1–1](#).

Figure 1–1: Study Schema

Abbreviations: C = cycle; D = day; EoT = End of treatment; FU = follow-up; i.v. = intra venous; LD = last dose; min = minute; q.d. = *quaque die* (once daily); Q4W = every 4 weeks

- a) Nivolumab 480 mg using a 30-min i.v. infusion every 4 weeks (Q4W). Regorafenib starting dose 80 mg orally every day (q.d.) for 21 days of each 28-day every 4 weeks (i.e. 21 days on, 7 days off). If starting dose is well tolerated (absence of any rash/HFSR any other or other Grade 2 or higher clinically significant toxicity) dose should be escalated to 120 mg orally daily starting with C2D1.
- b) Mandatory safety FU visit (at least 30 d after LD of regorafenib/nivolumab and 100 d after LD of nivolumab) and other active FU visits to collect safety and efficacy information for participants who discontinue study treatment without disease progression, if applicable.

Procedure	Screening		Treatment period ^a								EoT visit	Active FU		Long-term FU	Notes	
			Cycle1				Cycle 2			Cycle ≥3		30 d after LD of regorafenib and nivolumab ^b	100 d after LD for nivolumab ^b			
	within 28 d prior to first dose	within 7 d prior to first dose ^c	D 1	D 8	D15	D22	D1	D8	D15	D1	within 14 d after permanent discontinuation of regorafenib and nivolumab			every 3 months		
acceptable deviation				± 2 d			± 2 d			± 3 d		+ 7 d	+ 7 d	± 14 d		
AE review ^f	X	X	←=====→											Sections 8.3 and 10.3		
ECOG performance status	X	X	X				X			X	X	X	X		Section 8.2.5	
Serum pregnancy test if applicable (WOCBP only) ^g		X					X			X	X	X	X		Table 10–1	
Serology testing for Hepatitis B/C incl. HIV-1 (if applicable)	X		If clinically indicated													
Clinical chemistry ^h	X	X	X	X	X	X	X	X	X	X	X	X	X	X	Section 8.2.4	
Hematology	X	X	X	X	X	X	X	X	X	X	X	X	X	X	Table 10–1	
PT/INR and aPTT	X	X	X	If clinically indicated												
Urine analysis by dipstick ⁱ	X		X				X			X	X					
Thyroid function testing	X						X			X	X					
12-lead ECG	X										X			Section 8.2.3		
Vital signs (including weight)	X		X	X	X	X	X	X	X	X	X	X	X	Section 8.2.2		
Efficacy																
Tumor assessment (CT/MRI)	X									X	X	X	X	Section 8.1		
Survival status											X	X	X			

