- a) Note: The ± 2 d and ± 3 d assessment windows do not apply to collection of PK blood samples.
- b) A mandatory clinical visit to monitor safety will take place 30 d (window of +7 d) after the last administration of regorafenib/nivolumab and 100 d (window of +7 d) after the last dose of nivolumab, with the exception of death or withdrawal of consent.
- c) If tested within 7 days prior to first dose no additional testing on D1 required except for pregnancy testing and abnormal liver function tests.
- d) Contact IxRS to record the following: 1. to register the participant who has signed the PI/ICF (a unique participant identifier will be assigned), 2. the patient is a screening failure (failed to meet the criteria during the screening period), 3. on D1 of every treatment cycle so that the specific participant drug bottle/vial can be provided for dispensing purposes and also in case the participant has discontinued the study treatment (EOT) for any reason.
- e) Tumor genetic alteration(s), as determined by local testing results for MSI status, BRAF, extended RAS
- f) Participant will be followed for treatment related toxicities until these toxicities resolve, return to baseline or are deemed irreversible. All AEs will be documented for a minimum of 100 d after LD of nivolumab or 30 d after LD of regorafenib, whatever occurs later. CTCAE v5.0 will be used.
- g) Serum pregnancy test (for females of childbearing potential only). A negative pregnancy test must be available within 24 hr before study drug administration. Monthly pregnancy testing independent of study drug dosing should be conducted as per local regulations where applicable.
- h) Amylase and GGT will be assessed if clinically indicated.
- i) If protein dipstick result is 3+ or abnormal (based on type of urine test strip used), a laboratory urine analysis should be done for the quantification of proteinuria by urinary protein/creatinine ratio on a random urine sample preferably taken at mid-morning.

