4.1.3 Active Follow-Up

A mandatory clinical visit to monitor safety will take place 30 d (window of +7 d) after the last administration of regorafenib/nivolumab and 100 d (window of +7 d) after the last dose of nivolumab. Longer safety FU for nivolumab is required due to the long half-life of the antibody.

Participants who discontinue study intervention due to radiologically progressive disease will terminate the active FU period after the clinical safety visits.

Participants, who have not progressed clinically or radiologically or have discontinued study intervention for reasons other than death, withdrawal of consent or lost to FU, will continue with radiological tumor assessments. During the active follow-up period, CT (computed tomography) /MRI (magnetic resonance imaging) evaluations will be performed at the same intervals as during study treatment (every 8 weeks for the first year, and thereafter, every 12 weeks). In addition, study intervention-related toxicity/AE and information about survival status and subsequent anti-cancer therapy will be followed up until completion of the active FU.

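### The treatment-emergent laboratory window in SAP 6.5.5 has no visit tolerance, so on-schedule 100-day safety bloods drawn on days 101 to 107 drop out of those tables when both drugs stop together

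*SAP*

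**What the plan says.** **Analysis window.** SAP 6.5.5 states: "Clinical laboratory toxicities during treatment including a period of 30 days after last dose of treatment will be considered as" treatment-emergent for regorafenib. It adds: "The duration for Nivolumab will be 100 days". It gives no allowance for visit tolerance. It also does not say how the two limits combine in a single-arm table for patients who take both drugs.

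**Visit timing.** Protocol 1.3 (Schedule of Activities, footnote b) requires one safety visit "30 d (window of +7 d) after the last administration of regorafenib/nivolumab" and another "100 d (window of +7 d) after the last dose of nivolumab". Protocol 4.1.3 and Appendix 6 (10.6) repeat this. The footnote to the schema in 1.2 puts the visits "at least 30 d after LD of regorafenib/nivolumab and 100 d after LD of nivolumab", so nothing earlier is foreseen. Appendix 6 has one narrow exception: after a maximal interruption, the first follow-up visit is timed from permanent discontinuation.

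**Bloods.** In the Schedule of Activities, the chemistry and hematology rows are marked at the end-of-treatment, 30-day and 100-day visits. The thyroid row stops at end of treatment.

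**Purpose.** Protocol 4.1.3 explains the later visit: "Longer safety FU for nivolumab is required due to the long half-life of the antibody".

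**Other laboratory output.** SAP 6.5.5 summarizes values and changes from baseline by visit. SAP 4.1 lists all data. Unscheduled laboratory data are listed only (SAP 6.5.5; SAP 4.6 says the same of unscheduled visits).

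**The concern.** Each safety visit may start on the last day of the window of the drug it is timed to and may run seven days beyond it. A site that follows the protocol exactly will therefore often draw blood that the SAP then classes as not treatment-emergent. AEs are less exposed because they carry an onset date. A laboratory value has only its draw date.

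This matters most at day 100, because that visit exists to catch late nivolumab toxicity. A graded hepatic, renal or hematological abnormality first seen there on day 103 would be missing from the treatment-emergent incidence table. Protocol 8.2.4 requires clinically significant values to be repeated, but unscheduled repeats are only listed. Separately, because the SAP is silent on combining the two limits, two programmers could classify the same 30-day sample differently.

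**Working it through.** The plan gives no figure to reproduce. The check counts permitted visit days against the SAP limits.

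**Inputs**
- Laboratory limits: last regorafenib dose + 30 days; last nivolumab dose + 100 days (SAP 6.5.5).
- Visit tolerance: 0 to +7 days, so 8 permitted days per visit (Protocol 1.3, footnote b).
- Assumptions: day 30 and day 100 themselves count as inside, and visits are spread evenly over the 8 days.

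**Each visit against its own drug's limit.** One day is inside (day 30 or day 100). Outside: 7/8 = 87.5%. Without the even-spread assumption, the share outside is 1 minus the proportion of visits held exactly on the nominal day, which can be anything from 0% to 100%.

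**Both limits together.** Let g be the days from last nivolumab dose to last regorafenib dose, with g ≥ 0, and count days from last nivolumab. Let k = 0 to 7 be the visit delay.
- The 30-day visit is on day g + 30 + k. It is outside the regorafenib limit if k ≥ 1 and outside the nivolumab limit if g + 30 + k > 100. It is outside both if k ≥ max(1, 71 − g).
- The 100-day visit is on day 100 + k. It is outside the nivolumab limit if k ≥ 1 and outside the regorafenib limit if 100 + k > g + 30. It is outside both if k ≥ max(1, g − 69).

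| g (days) | 30-day visit outside both | 100-day visit outside both | Pooled over the two visits |
|---|---|---|---|
| 0 to 63 | 0/8 | 7/8 | 7/16 = 43.75% |
| 64 | 1/8 | 7/8 | 8/16 = 50% |
| 65 | 2/8 | 7/8 | 9/16 = 56.25% |
| 70 | 7/8 | 7/8 | 14/16 = 87.5% |
| 75 | 7/8 | 2/8 | 9/16 = 56.25% |
| 76 | 7/8 | 1/8 | 8/16 = 50% |
| 77 or more | 7/8 | 0/8 | 7/16 = 43.75% |

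**Both drugs stopped in the same cycle.** Nivolumab is given on day 1 and regorafenib on days 1 to 21, so g is 0 to 20. The 30-day visit then falls between day 30 and day 20 + 37 = 57 after last nivolumab, well inside 100 days. Only the 100-day visit is affected. If regorafenib stopped first, the 30-day visit is timed from last nivolumab and is again inside.

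**Regorafenib-specific analysis, g = 0.** The 30-day visit is 7/8 outside and the 100-day visit 8/8, pooled 15/16 = 93.75%.

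**Other scheduled bloods.** The end-of-treatment visit is within 14 days of permanent discontinuation and will usually lie inside the limits. The schedule has no further active follow-up blood visit between the 30-day and 100-day visits, and long-term follow-up starts only after active follow-up ends.

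**The Appendix 6 exception.** After a 28-day regorafenib interruption, the first follow-up visit is due within 14 days of discontinuation. That is about day 28 to 28 + 14 = 42 after the last regorafenib dose, so it can occasionally precede day 30.

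**The case against.** The strongest reply is that little is lost. Four parts of it stand.
- The values stay in by-visit descriptive statistics and in the subject listings. Clinically relevant changes must also be recorded as AEs (Protocol 8.2.4), and AEs are collected to the end of active follow-up (8.3.1).
- The 7/8 is a share of permitted visit days, not of toxicities missed. A patient's entry changes only if the first or worst abnormality appears in a late draw, and nothing in the documents says how often that happens.
- SAP 6.5.5 labels only some of its tables treatment-emergent. Whether the limit governs the change-in-worst-grade table is unstated. The liver tables in 6.5.5.1 are described as under nivolumab and have timings of their own.
- A nominal 30/100-day limit matches the one used for AEs (SAP 6.5.2) and deaths (SAP 6.5.3), so it is a coherent choice.

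These points limit the size but do not remove the gap. Means and medians by visit do not replace graded per-patient incidence. An asymptomatic abnormality first found on day 103 may miss the AE window too. Alignment with AEs and deaths is a modest benefit, since those events have onset dates. The hard limit also runs against SAP 4.3, which resolves ambiguous AE dates in favor of treatment-emergent.

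A reader might go further and infer that most of the follow-up bloods drop out. The documents do not support that. It applies the 30-day limit alone to the 30-day visit, although nivolumab's 100-day limit normally covers it.

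**Conclusion.** The mismatch is real but limited. When both drugs stop together, on-schedule 100-day bloods drawn on days 101 to 107 are excluded from the treatment-emergent laboratory tables. That is 7 of 8 permitted days, or 87.5% of such draws if visits are evenly spread. No other scheduled bloods fall inside the nivolumab window after the 30-day visit.

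The 30-day bloods are lost only from a regorafenib-specific analysis, or once nivolumab stopped roughly 65 days or more before regorafenib (the count starts at 64). If a value counts under either drug's limit, the pooled loss is 43.75% for same-cycle stops. It exceeds half only at gaps of 65 to 75 days.

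These shares rest on the even-spread assumption and on counting the nominal day as inside. They measure draws, not events. The effect on reported incidence is probably small, works only toward under-counting, and cannot be estimated from the documents. This is a cheap improvement to the SAP, not a threat to the trial's conclusions.

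**What to change.** In SAP 6.5.5:
1. Count laboratory values from the scheduled 30-day and 100-day safety visits as treatment-emergent anywhere within the 7-day visit tolerance; equivalently, set the limits to 37 days after last regorafenib and 107 days after last nivolumab. Then 0 of 8 permitted days of each visit fall outside the matching limit, instead of 7 of 8.
2. State that in the single-arm tables a value is treatment-emergent if it falls in either drug's window.

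The cost is a sentence or two and a change of date constants in the program. No visit or patient procedure changes. The downside is that the laboratory window becomes up to 7 days longer than the 30/100-day window for AEs and deaths, which a table footnote should state. Reported incidence can only stay the same or rise slightly.

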7. Adequate hematologic and organ function as assessed by the following laboratory tests performed within 7 d before treatment initiation:
 - Total bilirubin ≤ 1.5 x the upper limit of normal (ULN). Total bilirubin (≤ 3 x ULN) is allowed if Gilbert's syndrome is documented.
 - Alanine transaminase (ALT) and aspartate aminotransferase (AST) ≤ 3 x ULN (≤ 5 x ULN for patients with liver involvement of their cancer)
 - Platelet count $\geq 100,000$ /mm³, Hemoglobin (Hb) ≥ 9 g/dL, WBC ≥ 2000 / μ L absolute neutrophil count (ANC) ≥ 1500 /mm³

- Serum creatinine $\leq 1.5 \times$ ULN or creatinine clearance ≥ 40 mL/min (measured or calculated using the Cockcroft-Gault formula)
 - Prothrombin time-international normalized ratio (PT/INR) < 2.3 and activated partial thromboplastin time (aPTT) $< 1.5 \times$ ULN.
8. Measurable disease as determined by RECIST v1.1
 9. Provision of recent tumor tissue (as defined below) is mandatory for all participants at screening (Formalin-fixed paraffin-embedded block or minimum of 20 slides).
 - Tumor tissue obtained within 180 d of enrollment and after the last dose of most recent anti-cancer therapy
 - Or a new biopsy

Exceptions for patients with less than required tumor tissues may be considered after documented discussion and approval by the sponsor.

10. Anticipated life expectancy greater than 3 months
11. Be able to swallow and absorb oral tablets.
12. Women of childbearing potential (WOCBP) must agree to follow instructions for method(s) of contraception for the duration of study intervention and 210 d after last dose of regorafenib and 5 months after the last dose of nivolumab.

Males who are sexually active with WOCBP must agree to follow instructions for method(s) of contraception for the duration of study intervention and 120 d after last dose of regorafenib. In addition, male participants must be willing to refrain from sperm donation during this time.

Contraceptive use by men or women should be consistent with local regulations regarding the methods of contraception for those participating in clinical studies. Please refer to Section 10.4 for more information.

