9.4.5 Other Safety Analyse(s)

For all safety analyses, the FAS will be used as the FAS definition matches the one of the safety set. The incidence of TEAE (new or worsening from baseline) will be summarized by system organ class and preferred term, severity (based on CTCAE grades), type of AE and relation to study treatment. Deaths reportable as SAEs and non-fatal serious AEs will be listed by participant and tabulated by type of AE. AEs leading to study treatment discontinuation and/or modifications will be summarized. Laboratory abnormalities will be summarized by severity. Frequency and incidence rates will be provided. Frequency tables will also be provided for changes in severity from baseline to worst value post-baseline. Laboratory data considered as AE will be graded according to CTCAE v. 5.0, if applicable. The following summaries will be generated separately for hematology and biochemistry, overall and by cohort with the same dose:

- Frequency table for newly occurring on-treatment all CTCAE grades and CTCAE Grades 3 or 4
- Shift tables using CTCAE grades to compare baseline to the worst on-treatment value

CCI

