6.5.5.1 Laboratory abnormalities

Incidence tables for the following laboratory abnormalities under Nivolumab treatment will be summarized:

- ALT or AST > 3 x ULN
- ALT or AST > 5 x ULN
- ALT or AST > 10 x ULN
- ALR or AST > 20 x ULN
- Total bilirubin > 2 x ULN
- ALP > 1.5 x ULN
- Concurrent (within 1 day after Nivolumab treatment) ALT or AST > 3 x ULN and total bilirubin > 2 x ULN
- Concurrent (within 30 days after Nivolumab treatment) ALT or AST > 3 x ULN and total bilirubin > 2 x ULN
- TSH value > ULN and
 - with baseline TSH value \leq ULN
 - with at least one FT3/FT4 test value < LLN within 2-week window after the abnormal TSH test
 - with all FT3/FT4 test values \geq LLN within 2-week window after the abnormal TSH test
 - with FT3/FT4 missing within 2-week window after the abnormal TSH test
- TSH < LLN and
 - with baseline TSH value \geq LLN
 - with at least one FT3/FT4 test value > ULN within 2-week window after the abnormal TSH test
 - with all FT3/FT4 test values \leq ULN within 2-week window after the abnormal TSH test
 - with FT3/FT4 missing within 2-week window after the abnormal TSH test

6.5.6 12-Lead ECG, QTc

Analyses of ECG and QTc will be performed on the SAF population.

Corrected QT (QTc) will be calculated using Bazett's (QTcB) and Fridericia's (QTcF) formula. If several assessments are performed on the same day (without timing information) the average of the values will be considered.

Descriptive statistics including arithmetic mean, SD, median, minimum, and maximum will be presented for the following ECG parameters: HR, RR, PR, QT, QRS, QTcB and QTcF. Parameters will be summarized for actual results and the change from baseline for the safety analysis set at each scheduled visit.

The number and percent of patients with absolute QTc interval prolongation or QTc increase from baseline will be defined and summarized. The criteria are:

- QTc prolongation: QTc interval > 450 msec, QTc interval > 480 msec and QTc interval > 500 msec.
- Increase from baseline in QTc interval: QTc interval increases from baseline > 30 msec and QTc interval increases from baseline > 60 msec.

The number and percent of patients with new clinically significant abnormalities on ECGs per the investigator's assessment at post-baseline time points will be summarized.

Unscheduled ECG data will be listed (Section 16 of the CSR) only.

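### SAP 6.5.5 defines treatment-emergent laboratory toxicity by time window alone, so abnormalities present at entry that persist unchanged are counted, although protocol 9.4.5 plans a table of newly occurring grades

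*SAP*

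**What the plan says.** SAP 6.5.5 (Clinical laboratory data) gives the rule in two sentences. For regorafenib, "Clinical laboratory toxicities during treatment including a period of 30 days after last dose of treatment will be considered as" treatment-emergent. The next sentence adds: "The duration for Nivolumab will be 100 days". Neither sets a condition on the grade before treatment.

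The section then defines a laboratory baseline ("The last non-missing value before or on the first day of study drug will be retained as" baseline) but does not link it to the rule. It lists four sets of tables:

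- toxicity at screening;
- "Treatment-emergent hematological and biochemical toxicity";
- treatment-emergent toxicities with incidence above 5%;
- "Change in worst grade for hematological and biochemical toxicity from baseline".

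Protocol 9.4.5 (Other Safety Analyses) asks for two laboratory displays, for hematology and for biochemistry. One is a "Frequency table for newly occurring on-treatment all CTCAE grades and CTCAE Grades 3 or 4". The other is a set of shift tables from baseline to worst on-treatment grade. For adverse events, the same section takes treatment-emergent to mean new, or worse than at baseline.

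SAP 6.5.5.1 adds a separate list of threshold rows, introduced by "Incidence tables for the following laboratory abnormalities under Nivolumab treatment will be summarized". Its TSH rows include a baseline condition. Its ALT/AST, bilirubin and ALP rows do not.

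**The concern.** The protocol plans a frequency of new abnormalities and, separately, a shift table. The SAP's treatment-emergent incidence table takes the place of the first, but by its stated rule it counts every graded abnormality seen in the window, whether or not it was there before the first dose.

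This matters because the trial admits patients with abnormal laboratory values, safety of the combination is a secondary objective, and a single arm has no control group to show the background rate. Abnormalities from the cancer or from earlier treatment would then raise the incidences most likely to be read and cited. They would also affect which parameters reach the above-5% table.

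The SAP applies an onset or baseline condition elsewhere. An adverse event must start in the window (6.5.2), the TSH rows refer to baseline (6.5.5.1), and the ECG section counts new clinically significant findings (6.5.6).

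**Working it through.** The documents state no laboratory incidence, so there is no figure to reproduce. The check compares the two rules and then gives a scale.

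**1. Can patients enter with graded abnormalities?** Yes.

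- Inclusion criterion 7 allows ALT/AST up to 3 × ULN, and up to 5 × ULN "for patients with liver involvement of their cancer". It allows bilirubin up to 1.5 × ULN (3 × with documented Gilbert's syndrome), hemoglobin from 9 g/dL and platelets from 100,000/mm³.
- Exclusion criterion 4 bars unresolved Grade 2 or higher toxicity from prior therapy, but exempts anemia and lymphopenia.
- The SAP plans a table of graded toxicity at screening, which presupposes that some exists.

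**2. How is a patient classified whose entry grade stays the same throughout treatment?**

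- SAP 6.5.5: in the window, so treatment-emergent.
- Protocol 9.4.5: not newly occurring, so not counted.

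An abnormality that resolves before the first on-treatment sample is counted under neither rule. The gap concerns persistent abnormalities only.

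**3. Above-5% table.** With 70 treated patients, 3/70 = 4.3% and 4/70 = 5.7%. Four persistent baseline cases are enough, even with no new case.

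**4. Size of the overcount.** For one parameter, let b be the share of patients with a persistent baseline abnormality, q the rate of new onset among the others, and w the share of the b group who worsen.

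- SAP rule: b + (1 − b)q
- New-or-worse rule: (1 − b)q + bw
- Difference: b(1 − w), which is 70 × b × (1 − w) patients. It does not depend on q.

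The documents give none of b, q and w. The values below are assumptions.

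| b | w = 0 | w = 30% |
|---|---|---|
| 10% | 7 | 4.9 |
| 30% | 21 | 14.7 |
| 60% | 42 | 29.4 |

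Worked example with b = 30%, q = 20%, w = 10%:

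- SAP rule: 0.30 + 0.70 × 0.20 = 44% (30.8 of 70)
- New-or-worse rule: 0.14 + 0.30 × 0.10 = 17% (11.9 of 70)
- Difference: 70 × 0.30 × 0.90 = 18.9 patients

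The w = 0 column is also the overcount if newly occurring is read strictly, with worsening not counted.

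**5. Which rows of SAP 6.5.5.1 can be met at entry?** Compare each threshold with the eligibility caps.

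| Row | Can an eligible patient start above it? |
|---|---|
| ALT/AST > 3 × ULN | Yes, with liver involvement (cap 5 ×) |
| ALT/AST > 5, > 10, > 20 × ULN | No |
| Bilirubin > 2 × ULN | Only with documented Gilbert's syndrome (cap 3 ×) |
| ALP > 1.5 × ULN | Yes; criterion 7 sets no ALP limit |
| Both concurrent ALT/AST and bilirubin rows | Only with Gilbert's syndrome and liver involvement together |

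**The case against.** The best defense is that the information is not lost. The same SAP section plans a screening table and a change-in-worst-grade table, and a baseline-by-worst-grade display shows how many patients were new or worse. That stands, and it limits the consequence. But those tables answer the protocol's shift-table request. They leave the treatment-emergent incidence and above-5% counts as they are.

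A second defense is that the programmers may follow a convention that already requires worsening. SAP 4.3 does refer to standard guidelines, but for treatment-emergent adverse events. For laboratory data, 6.5.5 states its own rule.

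Third, the CTCAE thresholds are not reproduced in the documents, so one cannot confirm for every analyte that an unchanged entry value receives a grade. This stands as a limit on how many parameters are affected. It does not remove the problem: the exemption of anemia and lymphopenia in exclusion criterion 4 shows that graded abnormalities can be present at entry.

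Fourth, the tables are descriptive and no safety tests are planned. That is correct.

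A reader might go further and infer three things that the documents do not support:

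- **That all the liver rows of 6.5.5.1 share the fault.** The entry caps rule this out for the > 5, > 10 and > 20 × ULN rows and confine the bilirubin and concurrent rows to patients with Gilbert's syndrome. The protocol's request concerns CTCAE grades, not ULN thresholds, so no protocol commitment is broken in 6.5.5.1.
- **That entry abnormalities are reported as drug toxicity.** The laboratory tables carry no causality attribution. The drug-related tables are built from adverse events, with the investigator's attribution and onset in the window.
- **That the inflation equals b.** Against a new-or-worse rule it is b(1 − w), because patients who worsen are rightly counted.

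**Conclusion.** The point holds for the SAP 6.5.5 treatment-emergent incidence table and the above-5% table. The rule as written counts unchanged baseline abnormalities, and protocol 9.4.5 plans a count that leaves them out. This is a stated rule that gives the wrong count, not merely a missing detail.

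The size is 70 × b × (1 − w) patients per parameter: about 5 to 42 for the assumed b of 10–60% and w of 0–30%, and zero for a parameter with no persistent baseline abnormality. These figures are illustrations, since the documents give no baseline prevalence. The above-5% result (4 of 70) needs no such assumption beyond four persistent cases.

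In 6.5.5.1 the exposure is in practice limited to the ALT/AST > 3 × ULN and ALP > 1.5 × ULN rows, and a baseline sub-row there would be an improvement rather than a correction. The adverse-event tables and the primary endpoint are not affected.

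**What to change.** In SAP 6.5.5:

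- Define treatment-emergent laboratory toxicity as a CTCAE grade within the window (30 days for regorafenib, 100 days for nivolumab) that is higher than the baseline grade. If baseline is missing, count any grade and flag it.
- State that newly occurring in protocol 9.4.5 is read as new or worsened, because the protocol does not say whether worsening of an existing grade counts.
- Apply the definition to the treatment-emergent incidence table and the above-5% table. Keep the screening and change-in-worst-grade tables as planned.

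Optionally, in 6.5.5.1, add a sub-row for patients at or below the threshold at baseline to the ALT/AST > 3 × ULN and ALP > 1.5 × ULN rows, following the TSH rows. The > 5, > 10 and > 20 × ULN rows do not need one.

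The cost is a few lines of SAP text and one derived flag. Baseline grades are already needed for the change-in-worst-grade table, so no new data are collected.
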